**8.10 Hematologic Improvement or HI:**

All improvements must last at least 8 weeks. For a designated response (CR, PR HI) all relevant response criteria must be noted on at least two successive determinations at least one week apart after appropriate period following therapy.

**8.11 Erythroid response (HI-E):**

**Response:** For patients with pre-treatment Hb less than 11 Gm/dL, greater than 1.5Gm/dL increase in Hb; relevant reductions in units of RBC transfusion by an absolute number of at least 4 RBC transfusions/8wks compared with pre-treatment. Only RBC transfusions given for Hgb of < or = to 9.0g/dL pre-treatment will be count for transfusion response evaluation

#### **8.12 Platelet response (HI-P):**

**Response:** For patients with a pretreatment platelet count more than 200,000/ul, an absolute increase of 30,000/ul or more; for patients with a pretreatment platelet count less than 200,000/ul, a 100% or more increase in platelet count to more than 200,000/ul

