### **Peripheral blood evaluation: (absolute values must last at least 2 months).**

- Hemoglobin: greater than 11gm/dL (untransfused patient not on erythropoietin).
- Neutrophils: 1000/ul or more (not on a myeloid growth factor).
- Platelets: 100,000 ul or more (not on a thrombopoietic agent)
- Blasts: 0%.
- No dysplasia.

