#### **8.12 Absolute neutrophil response (HI-ANC):**

**Response:** For ANC less than 1000/ul before therapy at least a 100% increase or an absolute increase of 500/ul, whichever is greater.

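### Section 8.12 sets the platelet response (HI-P) cut-off at 200,000/µL, so patients starting below 100,000 can reach the plan's own CR platelet level and still count as non-responders

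*Combined protocol and SAP*

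**What the plan says.** Section 8.12 (HI-P) of the combined protocol and SAP has two branches. The upper one reads "For patients with a pretreatment platelet count more than 200,000/ul, an absolute increase of 30,000/ul or more". The lower one reads "for patients with a pretreatment platelet count less than 200,000/ul, a 100% or more increase in platelet count to more than 200,000/ul". Section 8.10 adds a duration rule, "All improvements must last at least 8 weeks", and asks for at least two successive determinations a week or more apart. Section 8.8 takes the baseline as the mean over the 4 weeks before therapy.

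The CR peripheral blood criteria in section 8.3 give these levels, each to last at least 2 months:

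- "Platelets: 100,000 ul or more (not on a thrombopoietic agent"
- "Neutrophils: 1000/ul or more (not on a myeloid growth factor"
- "Hemoglobin: greater than 11gm/dL (untransfused patient not on erythropoietin"

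The two neighbouring improvement rules are limited by baseline. HI-E in section 8.11 begins "For patients with pre-treatment Hb less than 11 Gm/dL, greater than 1.5Gm/dL increase in Hb". HI-ANC, also numbered 8.12, reads "For ANC less than 1000/ul before therapy at least a 100% increase or an absolute increase of 500/ul, whichever is greater".

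The Synopsis, section 5.2.2 and section 11.2 list the platelet response percentage among the secondary endpoints. Those places and section 8.1 name IWG 2006 as the response criteria. None of them states a different HI-P figure.

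**The concern.** An improvement category should be no harder to reach than the matching component of complete remission. Here it is harder for every patient who starts below 100,000/µL. The rule also applies to patients whose platelets are already well above the CR level, and it asks least of those just above 200,000. HI-E and HI-ANC do neither: their baseline limits of 11 g/dL and 1000/µL match their CR levels.

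Thrombocytopenic patients are expected in this trial. Entry requires only a count above 30,000/µL (section 6.2.1, item 11), section 6.1.1.3 refers to patients with existing thrombocytopenia, and Table 2 in section 6.5.3 has a separate row for baselines below 50,000/µL. Applied as written, HI-P would miss large sustained gains in these patients and count modest rises in patients without thrombocytopenia. The reported platelet response percentage would then not describe platelet improvement.

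**Working it through.** **Inputs** (units of 1,000/µL): HI-P cut-off c = 200, upper-branch rise 30, lower-branch rise 100% (section 8.12); CR platelet level 100 (section 8.3); entry floor above 30 (section 6.2.1).

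**Rise required from baseline b:**

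- b > c: at least 30.
- b < c and 2b > c: at least b, so the count must reach 2b.
- b < c and 2b ≤ c: strictly more than c − b, so the count must exceed c.
- b = c: no branch applies.

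**Results with c = 200 as printed:**

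| Baseline | Count needed | Rise needed | Multiple of baseline |
|---|---|---|---|
| 31 | > 200 | > 169 | > 200/31 = 6.45 |
| 40 | > 200 | > 160 | > 200/40 = 5.0 |
| 50 | > 200 | > 150 | > 200/50 = 4.0 |
| 80 | > 200 | > 120 | > 200/80 = 2.5 |
| 99 | > 200 | > 101 | > 200/99 = 2.02 |
| 150 | ≥ 300 | ≥ 150 | 2.0 |
| 199 | ≥ 398 | ≥ 199 | 2.0 |
| 200 | no rule | no rule | no rule |
| 201 | ≥ 231 | ≥ 30 | 231/201 = 1.15 |

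Every baseline in the Table 2 row below 50 needs a rise of more than 150. The baseline is a 4-week mean and can lie below the entry count: a mean of 25 needs more than 175.

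**Conflict with CR.** If b < 100, then 2b < 200, so the binding condition is a count above 200. Any count from 100 to 200 inclusive meets the CR platelet component and fails HI-P. A check of baselines 1 to 99 against final counts 100 to 200 in steps of 1 (99 × 101 = 9,999 pairs) found no exception. For example, 31 to 100 (+223%), 40 to 150 (+275%) and 50 to 200 (+300%) all fail, while 201 to 231 (+14.9%) passes if sustained. The duration rules in sections 8.3 and 8.10 are nearly the same (2 months and 8 weeks) and do not explain the gap.

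**Scale under other cut-offs.** The documents do not give the intended value. As an assumption only, for baselines of 31 to 99 and with b = c placed in the lower branch:

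- c = 20: a rise of 30 throughout.
- c = 50: a rise of 31 at b = 31, 40 at b = 40, 50 at b = 50, and 30 above 50. The range is 30 to 50.

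**The case against.** The strongest reply is that the plan names IWG 2006 as its standard. Section 11.2, which governs the analysis, cites IWG 2006 and not section 8.12, so an analyst could go to the source and never apply 200,000. No section gives 8.12 precedence over IWG 2006. This is fair as far as it goes: misclassification is a risk, not a certainty. But no section gives IWG 2006 precedence over 8.12 either, and 8.12 is the only working HI-P rule in the documents. Whoever uses another figure departs from the written definition.

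Four further points can be made.

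- The endpoint sentence speaks of major and minor responses, whereas 8.12 defines a single grade. This is true, but it is a further gap and not a defence, because no other text defines platelet response.
- Any two-branch rule jumps at its cut-off. With a cut-off of 50,000 the required rise drops from 50,000 to 30,000. With the wording used, a baseline exactly equal to the cut-off falls outside both branches whatever its value. The jump at 200,000 and the missing equality case are therefore weak evidence that the value is wrong. The conflict with CR carries the case, supported by the contrast with HI-E and HI-ANC.
- The impact is modest, since the endpoint is secondary and descriptive. This stands.
- The correct value cannot be read from the documents. This also stands, and it limits how specific the correction can be.

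**Conclusion.** The definition is wrong as written and should be corrected. The inconsistency follows from the plan's own text, without any outside source: HI-P asks more than the platelet component of CR for every baseline below 100,000/µL. The comparison is with that one component, not with full CR. The excess is large for thrombocytopenic patients, with a rise of more than 150,000 needed from any baseline below 50,000.

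The consequence is limited to a named descriptive secondary endpoint. The transfusion-independence rate and the sample size are unaffected. Whether the primary endpoint is touched cannot be said, because section 5.2.1 does not define responsiveness. The number of patients misclassified cannot be estimated without a baseline platelet distribution. That 200,000 is a ten-fold slip for 20,000 is an assumption, and the conclusion does not depend on it.

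**What to change.** In the HI-P definition of section 8.12, replace all three 200,000/µL figures with a single cut-off C, taken from the IWG 2006 criteria and checked against that source. Assign a baseline equal to C to one branch. Subject to the same check, limit the rule to baselines below the CR level of 100,000/µL. Suggested wording:

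> For patients with pretreatment platelets [below 100,000/µL, if confirmed against IWG 2006]: if more than C, an absolute increase of 30,000/µL or more; if C or less, a 100% or more increase to more than C.

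Make the change before responses are classified. It takes a few words and no new visits, tests or data, plus the company review and IRB approval that section 9.1 requires for an amendment.

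There are two side effects. The HI-P denominator becomes smaller if the 100,000 limit is confirmed. If C proves to be 20,000, few patients will fall in the doubling branch, because entry requires more than 30,000. That branch would not be impossible, because the baseline is a 4-week mean: hypothetical counts of 14,000, 16,000, 17,000 and 31,000 average 78,000/4 = 19,500.

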#### **8.12 Absolute neutrophil response (HI-ANC):**

**Response:** For ANC less than 1000/ul before therapy at least a 100% increase or an absolute increase of 500/ul, whichever is greater.

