### **6.2.2 Exclusion criteria**

1. Any serious medical condition, laboratory abnormality, or psychiatric illness that would prevent the subject from signing the informed consent form.
2. Pregnant or breast feeding females. (Lactating females must agree not to breast feed while taking lenalidomide).
3. Any condition, including the presence of laboratory abnormalities, which places the subject at unacceptable risk if he/she were to participate in the study or confounds the ability to interpret data from the study.
4. Any clinically significant cardiac disease, including congestive heart failure
5. Liver function studies including SGOT/SGPT > 3 x ULN
6. Clinically significant renal disease.
7. Any previous chemotherapy, hematopoietic growth factors, erythropoietin, or cytokines within 4 weeks of starting treatment. Note: prior therapy with G-CSF within 4 weeks is allowed.
8. Use of any other experimental drug or therapy within 28 days of baseline.
9. Known hypersensitivity to thalidomide.
10. The development of erythema nodosum if characterized by a desquamating rash while taking thalidomide or similar drugs.

---

† A female of childbearing potential is a sexually mature woman who: 1) has not undergone a hysterectomy or bilateral oophorectomy; or 2) has not been naturally postmenopausal for at least 24 consecutive months (i.e., has had menses at any time in the preceding 24 consecutive months).

11. Any prior use of lenalidomide. (Patients with prior therapy with thalidomide will be eligible as long as at least 4 weeks have elapsed between end of the drug and accrual on the present trial)
12. Concurrent use of other anti-cancer agents or treatments.
13. Known positive for HIV or infectious hepatitis, type B or C.
14. Life expectancy < 3 months

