### 6.5.3 Instructions for dose modifications or interruption during a cycle.

Table 2: Dose Modifications	
NCI CTC Toxicity Grade (unless otherwise noted)	Dose Modification Instructions
If baseline ANC ≥ 1000/ mm^3: Grade 3 neutropenia associated with fever (temperature ≥ 38.5° C) or Grade 4 neutropenia	
 
Hold (interrupt) lenalidomide dose.
 
Follow CBC weekly.
 
If neutropenia has resolved to ≤ grade 2 prior to Day 21, restart lenalidomide at next lower dose level and continue through the scheduled end of the cycle. Otherwise, omit for remainder of cycle and reduce the dose of lenalidomide by 1 dose level at the start of the next cycle. Omitted doses are not made up. If neutropenia is the only toxicity for which a dose reduction is required, G-CSF may be used and the lenalidomide dose maintained
 

If baseline ANC ≤ 1000/ mm^3: Grade 3 neutropenia associated with fever (temperature ≥ 38.5° C) or ANC < 50% of baseline	
 
Hold (interrupt) lenalidomide dose.
 
Follow CBC weekly.
 
If ANC has recovered to ≥50% of baseline and fever has resolved prior to Day 21, restart lenalidomide at next lower dose level and continue through the scheduled end of the cycle. Otherwise, omit for remainder of cycle and reduce the dose of lenalidomide by 1 dose level at the start of the next cycle. Omitted doses are not made up. If neutropenia is the only toxicity for which a dose reduction is required, G-CSF may be used and the lenalidomide dose maintained
 

If baseline platelet count ≥ 50,000/mm^3: Thrombocytopenia ≥Grade 3 (platelet count < 50,000/mm^3)	
 
Hold (interrupt) lenalidomide dose.
 
Follow CBC weekly.
 
If thrombocytopenia has recovered to ≤ grade 2 prior to Day 21, restart lenalidomide at next lower dose level and continue through the scheduled end of the cycle. Otherwise, omit for remainder of cycle and reduce the dose of lenalidomide by 1 dose level at the start of the next cycle. Omitted doses are not made up.
 

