#### **6.6.2 Prohibited concomitant therapy**

G-CSF is permitted for neutropenic fever and/or when clinically indicated.

Concomitant use of sargramostim (GM-CSF), other anti-cancer therapies, including radiation, thalidomide, or other investigational agents is not permitted while subjects are receiving study drug during the treatment phase of the study.

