**8.4 Partial remission (PR): (absolute values must last at least 2 months).**

All the CR criteria (if abnormal before treatment), except:

Bone marrow evaluation- blasts decrease by 50% or more over pretreatment but still >5%. Cellularity or morphology is not relevant.

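### The neutrophil response criterion (HI-ANC) lacks the growth-factor condition that the protocol applies to CR and PR, so a rise sustained on G-CSF can be scored as a response

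*Combined protocol and SAP*

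**What the plan says.** The neutrophil criterion is the second of the two sections numbered 8.12. In full it reads "For ANC less than 1000/ul before therapy at least a 100% increase or an absolute increase of 500/ul, whichever is greater". Section 8.10 adds two conditions for every hematologic improvement: it must last at least 8 weeks, and it must be seen on two successive determinations at least a week apart. Neither section mentions growth factors.

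The remission criteria do. The blood criteria for CR in Section 8.3 include "Neutrophils: 1000/ul or more (not on a myeloid growth factor", and Section 8.4 carries this into PR through "All the CR criteria (if abnormal before treatment), except".

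G-CSF is allowed at three points:

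- During treatment, Section 6.6.2: "G-CSF is permitted for neutropenic fever and/or when clinically indicated".
- In Table 2 of Section 6.5.3, in both baseline-ANC rows: "If neutropenia is the only toxicity for which a dose reduction is required, G-CSF may be used and the lenalidomide dose maintained".
- Before treatment, Section 6.2.2, exclusion 7: "Note: prior therapy with G-CSF within 4 weeks is allowed".

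Section 8.8 takes the baseline blood count as the mean over the 4 weeks before therapy. Sections 5.2.2 and 11.2 make the percentage of neutrophil responses a secondary endpoint. Section 11 has no rule for counts taken on G-CSF.

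**The concern.** G-CSF is given to raise the neutrophil count, and the neutrophil count is what HI-ANC measures. The protocol deals with this for CR and PR but leaves it open for the one response category that rests on neutrophils alone. Apart from the boundary value, the patients who can score HI-ANC are those in the Table 2 row for baseline ANC at or below 1000/mm3, where G-CSF is an option. Exposure is plausible: entry is open to any ANC above 250/ul (Section 6.2.1), and Section 6.1.1.3 says that neutropenia or thrombocytopenia occurred in most patients in the phase I/II experience.

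All patients receive single-agent lenalidomide, so no control arm can separate the effect of G-CSF from that of the study drug. What is at stake is whether the reported neutrophil response percentage can be read as lenalidomide activity.

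**Working it through.** The plan states no expected HI-ANC rate, so there is no figure to reproduce. The check compares the text and then illustrates the scale.

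**1. Where the growth-factor condition appears**

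| Response | Section | Growth-factor condition |
|---|---|---|
| CR, neutrophil line | 8.3 | Yes |
| PR | 8.4 | Yes, through the CR criteria |
| Any hematologic improvement | 8.10 | No |
| HI-ANC | 8.12 | No |
| Analysis of response | 11.2 | No |

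**2. What a response requires.** For baseline b below 1000/ul, the required count is b + max(b, 500).

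- b = 250: 250 + 500 = 750/ul
- b = 300: 300 + 500 = 800/ul
- b = 500: 500 + 500 = 1000/ul
- b = 800: 800 + 800 = 1600/ul

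The level must then hold for 8 weeks with confirmation. A patient who meets this while on repeated or continued G-CSF satisfies every written condition and is scored as a responder.

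**3. Effect through the baseline.** The window for permitted prior G-CSF coincides with the baseline window. Suppose, for illustration, that a patient's count off G-CSF is 300/ul and G-CSF lifts the 4-week mean to 600/ul. The required count moves from 800 to 600 + 600 = 1200/ul, and a real response can be missed. If the mean reaches 1000/ul or more, the patient leaves the HI-ANC category. This route lowers the response count.

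**4. Scale.** Let m be the number of patients with baseline ANC below 1000/ul. The documents do not give m; it cannot exceed the planned 56. Each G-CSF-driven response adds 100/m percentage points. The last column assumes two such responses and no true responders, with exact (Clopper-Pearson) 95% intervals.

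| m (assumed) | Points per G-CSF-driven response | Reported rate with two |
|---|---|---|
| 10 | 10.0 | 20.0% (2.5 to 55.6) |
| 20 | 5.0 | 10.0% (1.2 to 31.7) |
| 30 | 3.3 | 6.7% (0.8 to 22.1) |
| 56 | 1.8 | 3.6% (0.4 to 12.3) |

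Disregarding counts taken on G-CSF would return each of these rates to 0%. The number of G-CSF-driven responses is also an assumption, because the documents give neither the frequency nor the duration of G-CSF use.

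**The case against.** **Duration and confirmation already limit the problem.** This stands in part. Section 8.10 means that a short course for neutropenic fever would not normally produce a scored response. It does not exclude repeated or continued G-CSF, and Section 6.6.2 sets no limit on duration.

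**The Table 2 route is narrow.** This is fair. In the lower-baseline row the triggers are febrile grade 3 neutropenia or an ANC below half of baseline. Under the second trigger, a patient with baseline 300/ul has fallen below 150/ul and would have to reach 800/ul and hold it. The wider route is the general permission in Section 6.6.2.

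**IWG 2006 is cited, so its conditions apply anyway.** The documents do not bear this out. Section 8 writes out its own HI-ANC rule, and it prints the growth-factor condition where it wants it, in the CR criteria.

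**The consequence is small.** This largely stands. The primary endpoint is the expression profile (Section 5.2.1), the primary clinical efficacy parameter is transfusion independence (Section 8.1), and no hypothesis or sample size rests on neutrophil response.

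**Conclusion.** The omission is real and nothing in Section 8 or Section 11 repairs it. Followed as written, the plan scores a neutrophil rise sustained on G-CSF as a response in a single-arm trial, and G-CSF before entry can work in the opposite direction. The net direction and size cannot be determined from the documents. The figures of 1.8 to 10 points per affected patient rest on assumed values of m.

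A reader might infer four stronger claims, which the documents do not support:

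- That every G-CSF-related rise counts. The 8-week and confirmation rules exclude most short courses.
- That the rate is inflated by some stated amount, such as 10 to 30 points. That would need 10 to 30% of eligible patients on G-CSF throughout an 8-week window, all reaching the threshold and none responding otherwise; no such use is documented.
- That the bias is only upward. The baseline route runs the other way.
- That the main results are compromised. Transfusion independence and the signature endpoint are not directly affected.

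The point should be corrected, at the weight of one secondary percentage.

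**What to change.** Add to HI-ANC in Section 8.12 the growth-factor condition that the CR neutrophil line in Section 8.3 already carries. State in Section 11.2 that ANC values taken on G-CSF count neither towards the 4-week baseline mean nor towards meeting or sustaining the HI-ANC threshold. Report how many patients are affected. Add a sensitivity analysis that scores any patient with G-CSF in the response window as a non-responder. Making that stricter rule the main analysis is debatable, since one brief course could turn a true responder into a failure.

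The cost is one phrase and one analysis rule. Prior medications over 28 days and concomitant therapies are already recorded (Sections 2 and 6.1.1), and counts are weekly in Cycles 1 to 3. The team should confirm that the case report form captures G-CSF start and stop dates. The HI-ANC rate may be lower. A few patients may become not evaluable for it, because Section 2 schedules few counts before treatment and disregarding those taken on G-CSF may leave no baseline. The rules on when G-CSF may be given are not changed.

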### **9 Protocol Amendments/Deviations**

#### **9.1 Protocol amendments**

Any amendment to this protocol must be agreed to by the Principal Investigator and reviewed by Celgene. Amendments should only be submitted to IRB/EC after consideration of Celgene review. Written verification of IRB/EC approval will be obtained before any amendment is implemented.

#### **9.2 Protocol deviations**

When an emergency occurs that requires a deviation from the protocol for a subject, a deviation will be made only for that subject. A decision will be made as soon as possible to determine whether or not the subject (for whom the deviation from protocol was effected) is to continue in the study. The subject's medical records will completely describe the deviation from the protocol and state the reasons for such deviation. In addition, the Investigator will notify the IRB/EC in writing of such deviation from protocol.

Non-emergency minor deviations from the protocol will be permitted with approval of the Principal Investigator.

### **10 Data Management**

#### **10.1 Data Collection:**

Study-specific case report forms will be created to capture protocol information.

## **10.2 Analyses and Reporting**

Data will be analyzed and reported after accrual is completed. All subsequent data collected will be analyzed and reported in a follow-up clinical report.

## **10.3 Data Monitoring Committee**

The Data Monitoring Committee (DMC) will be composed of medical and statistical independent reviewers and will meet to review the efficacy and safety data and determine a risk/benefit analysis in this subject population. The purpose of the DMC is to advise on serious safety considerations, lack of efficacy and any other considerations within the charge to the Committee. The DMC may request additional meetings or safety reports as deemed necessary upon discussion with Celgene and its representatives. The DMC may stop the study following review of results from each interim analysis. The first interim analysis will examine only safety information; the second interim, conducted when the database is more mature, will examine both safety and efficacy. Appropriate efficacy and safety data summaries will be provided to the DMC after each interim analysis.

